6.2 Secondary Safety Endpoints

1. The Primary Safety Endpoint assessed at 7 rather than 30 days
2. The proportion of subjects with a device- or procedure-related SAE
3. The proportion of subjects with stroke or TIA
4. The proportion of subjects requiring cardioversion
5. The proportion of subjects requiring an arrhythmia-related hospitalization

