7.3 Device Effects

7.3.1 Adverse Device Effects

An Adverse Device Effect (ADE) is an adverse event related to the use of an investigational medical device

- NOTE 1: This definition includes adverse events resulting from insufficient or inadequate instructions for use, deployment, implantation, installation, or operation, or any malfunction of the investigational medical device.
- NOTE 2: This definition includes any event resulting from use error or from intentional misuse of the investigational medical device.
- NOTE 3: “Related to the uses of an investigational medical device” shall be defined for this protocol as a determination that the effects was probably or definitely related to an investigational device.

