7.7 Causality Relationship

The investigator will assess the causality of all adverse events in relation to the investigational device or any other study-related procedures according to five different levels of causality:

1) Not related: relationship to the device or procedures can be excluded when:

- the event is not a known side effect of the product category the device belongs to or of similar devices and procedures;
- the event has no temporal relationship with the use of the investigational device or the procedures;

- the serious event does not follow a known response pattern to the medical device (if the response pattern is previously known) and is biologically implausible;
- the discontinuation of medical device application or the reduction of the level of activation/exposure - when clinically feasible – and reintroduction of its use (or increase of the level of activation/exposure), do not impact on the serious event;
- the event involves a body-site or an organ not expected to be affected by the device or procedure;
- the serious event can be attributed to another cause (e.g. an underlying or concurrent illness/ clinical condition, an effect of another device, drug, treatment or other risk factors);
- harms to the subject are not clearly due to use error;
- In order to establish the non-relatedness, not all the criteria listed above might be met at the same time, depending on the type of device/procedures and the serious event.

2) Unlikely: the relationship with the use of the device seems not relevant and/or the event can be reasonably explained by another cause, but additional information may be obtained.

3) Possible: the relationship with the use of the investigational device is weak but cannot be ruled out completely. Alternative causes are also possible (e.g. an underlying or concurrent illness/ clinical condition or/and an effect of another device, drug or treatment). Cases were relatedness cannot be assessed or no information has been obtained should also be classified as possible.

4) Probable: the relationship with the use of the investigational device seems relevant and/or the event cannot reasonably have explained by another cause, but additional information may be obtained.

5) Causal relationship: the serious event is associated with the investigational device or with procedures beyond reasonable doubt when:

- the event is a known side effect of the product category the device belongs to or of similar devices and procedures;

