IF (7≤ (EVENT DATE-PROCEDURE DATE IN PROCEDURAL DATA FORM (PR)) **OR** (7≤ (EVENT DATE-REMAPPING DATE IN FOLLOW-UP 3D ELECTROANATOMICAL MAPPING FORM (RM)) **AND** PRIMARY SAFETY ENDPOINT EVENT CRITERIA=' Vascular Access Complication' **THEN** Vascular Access Complication = 'Yes'.
ELSE Vascular Access Complication = 'No'.
- Derived criteria "Total Early Onset Composite Safety Endpoint assessed at 7 days" will be defined as follows:
IF Death 7 days='Yes' **OR** Myocardial infarction 7 days='Yes' **OR** Diaphragmatic Paralysis 7 days='Yes' **OR** TIA 7 days='Yes' **OR** CVA 7 days='Yes' **OR** Major pericarditis 7 days='Yes' **OR** Tamponade/Perforation 7 days='Yes' **OR** Heart Block 7 days='Yes' **OR** New or Prolonged Hospitalization, excl. AF/AFL 7 days='Yes' **OR** Vascular Access Complication 7 days='Yes' **THEN** Total Early Onset Composite Safety Endpoint assessed at 7 days = 'Yes'.
ELSE Total Early Onset Composite Safety Endpoint assessed at 7 days = 'No'.
- Derived criteria "Device-Related Serious Adverse Events (SAEs)" will be defined as follows:
IF CEC seriousness ="Serious" **AND** CEC relationship to study Device in (Causal relationship, Probably related, Possibly related, Unlikely to be related) in adverse event adjudication form **THEN** Device-Related Serious Adverse Events (SAEs)='Yes'; **ELSE** Device-Related Serious Adverse Events (SAEs)='No'
- Derived criteria "Procedure-Related Serious Adverse Events (SAEs)" will be defined as follows:
IF CEC relationship to study procedure in (Causal relationship, Probably related, Possibly related, Unlikely to be related) **AND** CEC seriousness ='Serious' **THEN** Procedure-Related Serious Adverse Events (SAEs)='Yes'
ELSE IF CEC relationship to study procedure ='Not related' **AND** CEC seriousness =" Serious" **THEN** Procedure-Related Serious Adverse Events (SAEs)='No'
- Derived criteria "Cardioversion" will be defined as follows:
IF Arrhythmia-Treatment DC Cardioversion is ticked in **Arrhythmia episodes form** **THEN** Cardioversion ='Yes';
ELSE Cardioversion ='No'

CONFIDENTIEL / CONFIDENTIAL

Toute reproduction ou distribution, totale ou partielle, de ce document, sans autorisation préalable de ICON PLC est interdite.
Reproduction and distribution of this document, in whole or in part, is strictly forbidden without prior authorization from ICON PLC.

	STATISTICAL ANALYSIS PLAN	FARAPULSE PersAFOne SAP V1.0 PERSAFONE Page 31 /49
---	----------------------------------	--

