4.1.12. Table 12. Secondary Safety Endpoints

	ITT Population N = XX	
	n/N (%)	[95% CI]
Primary Safety Endpoint (Early and Late Onset Composite Safety Endpoint) assessed at 7 days	XX/XX (XX.X%)	[XX% - XX%]
Total Early (within 30 days of Index or Remap Procedure)	XX/XX (XX.X%)	[XX% - XX%]
Death	XX/XX (XX.X%)	[XX% - XX%]
Myocardial infarction (MI)	XX/XX (XX.X%)	[XX% - XX%]
Persistent diaphragmatic paralysis	XX/XX (XX.X%)	[XX% - XX%]
Stroke	XX/XX (XX.X%)	[XX% - XX%]
Transient ischemic attack (TIA)	XX/XX (XX.X%)	[XX% - XX%]
Peripheral or organ thromboembolism	XX/XX (XX.X%)	[XX% - XX%]
Pericarditis	XX/XX (XX.X%)	[XX% - XX%]
Cardiac tamponade / perforation	XX/XX (XX.X%)	[XX% - XX%]
Vascular access complications requiring intervention	XX/XX (XX.X%)	[XX% - XX%]
Heart block	XX/XX (XX.X%)	[XX% - XX%]
Total Late (any time during follow-up through 12 months)	XX/XX (XX.X%)	[XX% - XX%]

CONFIDENTIEL / CONFIDENTIAL

Toute reproduction ou distribution, totale ou partielle, de ce document, sans autorisation préalable de ICON PLC est interdite.
Reproduction and distribution of this document, in whole or in part, is strictly forbidden without prior authorization from ICON PLC.

ICON	STATISTICAL ANALYSIS PLAN	FARAPULSE PersAFOne SAP V1.0 PERSAFONE Page 43 /49
-------------	----------------------------------	--

Pulmonary vein (PV) stenosis (> 70% diameter reduction from baseline)	XX/XX (XX.X%)	[XX% - XX%]
Atrio-esophageal fistula	XX/XX (XX.X%)	[XX% - XX%]
Device-Related Serious Adverse Events (SAEs)	XX/XX (XX.X%)	[XX% - XX%]
Procedure-Related Serious Adverse Events (SAEs)	XX/XX (XX.X%)	[XX% - XX%]
Stroke	XX/XX (XX.X%)	[XX% - XX%]
Transient Ischemic Attack (TIA)	XX/XX (XX.X%)	[XX% - XX%]
Cardioversion	XX/XX (XX.X%)	[XX% - XX%]
Arrhythmia-related (AF, AFL, AT) hospitalization	XX/XX (XX.X%)	[XX% - XX%]

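### The SAP counts SAEs adjudicated as Unlikely to be related as device-related and procedure-related, and never computes the combined related-SAE endpoint

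*SAP*

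**What the plan says.** The second secondary safety endpoint in Protocol 6.2 is "The proportion of subjects with a device- or procedure-related SAE". SAP 2.4.8.2 repeats it. Neither place says which causality levels count as related.

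SAP 2.5 supplies that rule in two separate derivations, both for events adjudicated as serious:

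- Device: Yes if "CEC relationship to study Device in (Causal relationship, Probably related, Possibly related, Unlikely to be related"; anything else is No.
- Procedure: Yes if "CEC relationship to study procedure in (Causal relationship, Probably related, Possibly related, Unlikely to be related"; No only if the level is Not related.

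The protocol has its own language for relatedness. Section 7.7 grades events "according to five different levels of causality". The second-lowest level, Unlikely, is described this way: "the relationship with the use of the device seems not relevant and/or the event can be reasonably explained by another cause". Section 7.3.1 Note 3 fixes what related to the investigational device means for this protocol, namely a "determination that the effects was probably or definitely related to an investigational device". Section 7.3.3 Note 2 applies the same cut to SAEs when identifying unanticipated serious device effects.

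SAP Table 12 (4.1.12) prints one row for device-related SAEs and one for procedure-related SAEs. It has no row for the two combined.

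**The concern.** An SAE that the adjudicators thought was reasonably explained by something else would be printed under a heading that says it was caused by the device or the procedure. As programmed, each row comes close to reporting any SAE for which a relationship was not positively excluded. Such a rate is not the one the protocol describes, and it cannot be compared with a rate from another study that used a probable-or-definite cut.

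The second problem does not depend on the first. The protocol asks for one number per subject population: how many subjects had an SAE related to the device, the procedure or both. Whatever threshold is chosen, that number has no derived variable in SAP 2.5 and no line in the output.

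**Working it through.** There is no stated rate or sample-size calculation to reproduce; both documents say the study has no formal hypothesis test. The check is therefore a comparison of rules, followed by an illustration of size.

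**Step 1: set the rules side by side.** Two readings are assumed. The adjudication form is taken to use the five levels of Protocol 7.7, since the two SAP rules between them name all five. Definitely in Note 3 is taken to be the top level, Causal relationship.

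| Level | SAP device rule | Protocol 7.3.1 Note 3 (device) | SAP procedure rule | Protocol (procedure) |
|---|---|---|---|---|
| Causal | Yes | Yes | Yes | no cut-off stated |
| Probable | Yes | Yes | Yes | no cut-off stated |
| Possible | Yes | No | Yes | no cut-off stated |
| Unlikely | Yes | No | Yes | no cut-off; 7.7 meaning speaks against |
| Not related | No | No | No | No |

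For the device, the SAP set {Causal, Probable, Possible, Unlikely} strictly contains the protocol set {Causal, Probable}. So the SAP count is never below the protocol count, and exceeds it by every subject whose SAEs reach only Possible or Unlikely. Removing Unlikely alone would not bring the device rule into line.

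For the procedure, the conflict is confined to Unlikely. It rests on the meaning of that level in 7.7, whose wording there speaks of the device although the scale is introduced for device and procedures alike.

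**Step 2: size per subject.** If k subjects enter a row only through wrongly included levels, the row rises by k/N. With N = 40 (Protocol 3.7, an upper limit), 1/40 = 2.5 percentage points. With N = 25, the figure printed in the shells of SAP Tables 5 and 19, 1/25 = 4.0 points.

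The documents give no causality counts, so k is an assumption, shown here from 0 to 3 with no subject meeting the protocol definition. Intervals follow SAP 2.1.4, taking the asymptotic conditions to fail at such small counts: Agresti-Coull at 0%, exact otherwise.

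| k | N = 40 (95% CI) | N = 25 (95% CI) |
|---|---|---|
| 0 | 0/40 = 0.0% (0.0-10.4) | 0/25 = 0.0% (0.0-15.8) |
| 1 | 1/40 = 2.5% (0.1-13.2) | 1/25 = 4.0% (0.1-20.4) |
| 2 | 2/40 = 5.0% (0.6-16.9) | 2/25 = 8.0% (1.0-26.0) |
| 3 | 3/40 = 7.5% (1.6-20.4) | 3/25 = 12.0% (2.5-31.2) |

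If one subject does meet the protocol definition, k = 3 moves the row from 1/40 = 2.5% (0.1-13.2) to 4/40 = 10.0% (2.8-23.7).

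This arithmetic applies row by row. In a combined row, a subject rated Unlikely for the device but Probable for the procedure belongs there anyway. Only subjects who qualify on neither count would be added wrongly.

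**Step 3: can the endpoint be recovered from the two rows?** Let D and P be the subjects in the device and procedure rows. The combined count lies between max(D, P) and min(D + P, N). For illustration, D = 2 and P = 3 at N = 40 gives anything from 3/40 = 7.5% to 5/40 = 12.5%. The rows alone do not determine the endpoint.

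**The case against.** The best defence is that a wide rule is cautious. It can only make the device look worse, it is written down in advance, and the adjudicated level is captured, so a reader with the data could undo it. The endpoint is secondary and descriptive in a single-arm feasibility study. All of that stands, and it lowers the priority. It does not make the row correct. Nor does caution need Unlikely: Protocol 7.7 already sends events that cannot be assessed, or that lack information, to Possible.

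The same sentence in 7.7 is a fair warning against overcorrecting. A Causal-or-Probable cut would drop unassessable SAEs from the headline. For the device, Note 3 supports that cut; for the procedure, nothing does. A reader might infer that the protocol's definition of related governs both rows, but Notes 7.3.1(3) and 7.3.3(2) speak only of the device.

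The SAP also says it was written against protocol Revision C, while the protocol supplied is Revision E. Whether Revision C contained Note 3 cannot be seen. The mismatch with the current protocol is certain; a departure from the text the SAP authors had in hand is not shown.

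**Conclusion.** The SAP's device-related rule contradicts the protocol at two levels, Possible and Unlikely. Its procedure-related rule conflicts with the meaning of one level, Unlikely. The error has a known direction, upwards and against the device, and a known unit: 2.5 percentage points per affected subject at N = 40. Its total is unknown and could be zero, if no subject's SAEs stop at those levels. Separately, and at any threshold, the endpoint as worded is never computed. Both should be corrected before analysis, as a moderate matter for a secondary descriptive endpoint.

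Three stronger conclusions are tempting and are not supported:

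- **That the inflation can be sized from the earlier studies.** Protocol 1.3 reports re-hospitalisation for atrial arrhythmia in 3/40 = 7.5% and 3/60 = 5.0% of patients, but gives no causality ratings. Protocol 4.1 lists arrhythmia as an anticipated complication, which could equally support a higher rating.
- **That the report will contradict its own tabulation of serious adverse device effects.** The SAP plans no such table or listing. The conflict is with the protocol's definitions.
- **That the primary safety result is affected.** The composite is derived from a separate adjudication field naming the endpoint criterion, not from this rule. SAP Table 15 also reports all SAEs irrespective of cause.

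**What to change.** In SAP 2.5:

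1. Remove Unlikely to be related from both rules.
2. Set the device-related rule to Causal or Probable, citing Protocol 7.3.1 Note 3.
3. State one explicit threshold for procedure-related and apply it. Possible or higher, or the same cut as the device, are both defensible. The choice is the sponsor's because the protocol makes none.
4. Derive one combined variable per subject: at least one SAE that is device-related or procedure-related.
5. Write the No branch the same way in both rules. At present an absent device rating becomes No while an absent procedure rating is left undefined, although the opening of 2.5 says a derivation with a missing component is itself missing.

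In SAP Table 12, make the combined variable the endpoint row, with the two component rows beneath it. Always show a labelled row that also includes Possibly related, or tabulate SAEs by causality level.

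The cost is SAP wording, a few lines of programming and a few more table rows. No new data are needed because the adjudicated level is already captured. The headline rate becomes less cautious, which the mandatory Possible row covers.

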5.2 Control of Systematic Error and Bias

Subjects are not randomized in this single arm study and therefore masking is not achievable. Error and bias are being controlled by several means, including a comprehensive set of study procedures as defined in the protocol to ensure consistent management and outcome measure assessment. Follow-up Holter monitoring and event monitoring data, and all MRI/CT dimensions of PVs, will be assessed objectively by third parties according to standard clinical protocols. Primary effectiveness and safety outcomes will be reviewed by an independent Clinical Events – Data Monitoring Committee (CEDMC). A complete Study Report will allow scientific and clinical reviewers to independently assess potential error and bias.

Study outcomes will be reviewed and adjudicated by an independent Clinical Events and Data Monitoring Committee (CEDMC) more fully described in **Section 9.10, Clinical Events and Data Monitoring Committee.**

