9.10 Clinical Events and Data Monitoring Committee

The Sponsor has established an external group of expert physicians who are not investigators to serve as the Clinical Events and Data Monitoring Committee (CEDMC). This group will consist of a panel of 3 experienced, independent physicians who are not investigators and who will be supported by the Medical Monitor and Study Statistician. A combined CEDMC procedure is an appropriate structure for a 40 subject feasibility study.

The CEDMC will review and approve a Charter. The CEDMC will convene during the study to screen, classify and adjudicate all adverse events reported in the subject investigation as well as major study outcomes. The CEDMC will be provided with case summaries, relevant source documents and any other information required to evaluate and adjudicate the adverse events and study outcomes.

The CEDMC will also convene to review safety data and trends during the conduct of the study. This formal assessment will occur at a minimum after the enrollment of 20 and then 40 subjects. The CEDMC will recommend to the Sponsor whether a study pause or termination is required if it identifies a trend that indicates a danger to patient safety.

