2.1.2. Handling Missing Data

In order to provide unbiased and informative findings, no replacement of missing values is planned for any parameters. Analyses is performed with all available data only.

Data collected by the Investigators and reviewed by the Clinical Event Committee (CEC):

CONFIDENTIEL / CONFIDENTIAL

Toute reproduction ou distribution, totale ou partielle, de ce document, sans autorisation préalable de ICON PLC est interdite.
Reproduction and distribution of this document, in whole or in part, is strictly forbidden without prior authorization from ICON PLC.

	STATISTICAL ANALYSIS PLAN	FARAPULSE PersAFOne SAP V1.0 PERSAFONE Page 13 /49
---	----------------------------------	--

When the data are collected by the investigators and reviewed by the CEC, the analysis will be as follows:

- The data reviewed by the CEC will prevail and will be analysed with no replacement of missing data from the CEC with the data collected by the investigator

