COUNT of [(Left Superior Isolated/Blocked ='Yes', Left Inferior Isolated/Blocked='Yes', Left Common Ostium Isolated/Blocked='Yes', Right Middle Isolated/Blocked='Yes', Right Superior Isolated/Blocked='Yes', Right Inferior Isolated/Blocked='Yes')] / COUNT of [(Left Superior Isolated/Blocked in (Yes, No) , Left Inferior Isolated/Blocked in (Yes, No), Left Common Ostium Isolated/Blocked in (Yes, No), Right Middle Isolated/Blocked in (Yes, No), Right Superior Isolated/Blocked in (Yes, No), Right Inferior Isolated/Blocked in (Yes, No))] **in Procedural data form (PR)**
- Derived criteria "Proportion of all ablated pulmonary veins isolated using the study device during the Index Procedure that remain isolated at the 75-day remapping procedure" will be defined as follows:
(Derived criteria "Total number of veins isolated" - Derived criteria "Number of veins with gaps")/ Derived criteria "Total number of veins isolated"
- Derived criteria Proportion "Chronic CTI at 75d remap" will be defined as follows:
IF CTI lesion durable ='Yes' **in Follow-up 3D electroanatomical mapping form (RM)** **THEN** Chronic CTI at 75d remap ='Yes'
ELSE IF CTI lesion durable ='No' **in Follow-up 3D electroanatomical mapping form (RM)** **THEN** Chronic CTI at 75d remap ='No'
- Derived criteria Proportion "LAPW chronic isolation" will be defined as follows:
IF Anatomical Structure/Area other specification 1 **IN** ("POSTERIOR WALL" "LA POSTERIOR WALL" "LAPW" "PA WALL" "BOX POSTERIOR WALL") **AND** Other 1 Lesion durable = 'yes' **OR** Anatomical Structure/Area other specification 2 **IN** ("POSTERIOR WALL" "LA POSTERIOR WALL" "LAPW" "PA WALL" "BOX POSTERIOR WALL") **AND** Other 2 Lesion durable = ='Yes' **in Follow-up 3D electroanatomical mapping form (RM)** **THEN** LAPW chronic isolation= 'Yes'

CONFIDENTIEL / CONFIDENTIAL

Toute reproduction ou distribution, totale ou partielle, de ce document, sans autorisation préalable de ICON PLC est interdite.
Reproduction and distribution of this document, in whole or in part, is strictly forbidden without prior authorization from ICON PLC.

	STATISTICAL ANALYSIS PLAN	FARAPULSE PersAFOne SAP V1.0 PERSAFONE Page 26 /49
---	----------------------------------	--

ELSE LAPW chronic isolation = 'No'

Primary Safety endpoint

Unless otherwise indicated, all the following variables will be derived from the Adverse event adjudication form (CE)

- Derived criteria "Death" will be defined as follows:

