- Derived criteria “Stroke after index procedure” will be defined as follows:
IF Event name='STROKE' in **Adverse event form** **AND** Event start date ≥ Procedure date in **Procedural data Form (PR)** **THEN** STROKE='Yes'
ELSE STROKE='No'
- Derived criteria “Transient Ischemic Attack (TIA) after index procedure” will be defined as follows:
IF Event name=' Transient Ischemic Attack' in **Adverse event form** **AND** Event start date ≥ Procedure date in **Procedural data Form (PR)** **THEN** TIA='Yes'
ELSE TIA='No'
- Derived criteria “Stroke after Remap procedure” will be defined as follows:
IF Event name='STROKE' in **Adverse event form** **AND** Event start date ≥ Remap date IN **FOLLOW-UP 3D ELECTROANATOMICAL MAPPING FORM (RM)** **THEN** STROKE='Yes'
ELSE STROKE='No'
- Derived criteria “Transient Ischemic Attack (TIA) after Remap procedure” will be defined as follows:
IF Event name=' Transient Ischemic Attack' in **Adverse event form** **AND** Event start date ≥ Remap date in **FOLLOW-UP 3D ELECTROANATOMICAL MAPPING FORM (RM)** **THEN** TIA='Yes'
ELSE TIA='No'
- Derived criteria “Arrhythmia-related (AF, AFL, AT) hospitalization” will be defined as follows:
IF Arrhythmia-related (AF, AFL, AT) hospitalization ='Yes' in **MDT excel file** **THEN** Arrhythmia-related (AF, AFL, AT) hospitalization ='Yes'
ELSE IF Arrhythmia-related (AF, AFL, AT) hospitalization ='No' in **MDT excel file** **THEN** Arrhythmia-related (AF, AFL, AT) hospitalization ='No'
- Derived criteria “Death” will be defined as follows:
IF SAE: Death='Yes' in **Adverse event form** **OR** Reason ='Patient death' in **study exit form** **THEN** Death='Yes'
ELSE Death='No'

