4.1.3. Table 3. Baseline Medical History

	ITT Population	
	Mean±S.D.	Median (min, max) (Q1, Q3)
	XX±X XX (XX, XX) (XX, XX)	[95% CI]
Left atrial diameter (cm)	XX±X XX (XX, XX) (XX, XX)	[XX - XX]
AF history (number of months)	XX±X XX (XX, XX) (XX, XX)	[XX - XX]
LVEF (%)	XX±X XX (XX, XX) (XX, XX)	[XX - XX]
CHA2DS2VASC	XX±X XX (XX, XX) (XX, XX)	[XX - XX]
	n/N (%)	[95% CI]
Patient that failed any AAD	XX/XX (XX.X%)	[XX% - XX%]
If Yes: Class I	XX/XX (XX.X%)	[XX% - XX%]

CONFIDENTIEL / CONFIDENTIAL

Toute reproduction ou distribution, totale ou partielle, de ce document, sans autorisation préalable de ICON PLC est interdite.
Reproduction and distribution of this document, in whole or in part, is strictly forbidden without prior authorization from ICON PLC.

STATISTICAL ANALYSIS PLAN

FARAPULSE PersAFOne SAP V1.0

PERSAFONE

Page 34 /49

If Yes: Beta Blocker/Class II	XX/XX (XX.X%)	[XX% - XX%]
If Yes: Class III	XX/XX (XX.X%)	[XX% - XX%]
If Yes: Calcium Channel Blocker/Class IV	XX/XX (XX.X%)	[XX% - XX%]
Smoking	XX/XX (XX.X%)	[XX% - XX%]
Dyslipidemia	XX/XX (XX.X%)	[XX% - XX%]
COPD	XX/XX (XX.X%)	[XX% - XX%]
PPM/ICD	XX/XX (XX.X%)	[XX% - XX%]
Unstable angina	XX/XX (XX.X%)	[XX% - XX%]
NYHA Heart Failure	XX/XX (XX.X%)	[XX% - XX%]
Class I	XX/XX (XX.X%)	[XX% - XX%]
Class II	XX/XX (XX.X%)	[XX% - XX%]
Class III	XX/XX (XX.X%)	[XX% - XX%]
Class IV	XX/XX (XX.X%)	[XX% - XX%]
Any History of Structural heart disease	XX/XX (XX.X%)	[XX% - XX%]
If yes: Cardiomyopathy	XX/XX (XX.X%)	[XX% - XX%]
If yes: Coronary artery disease	XX/XX (XX.X%)	[XX% - XX%]
If yes: Aneurysm	XX/XX (XX.X%)	[XX% - XX%]
If yes: Left ventricular hypertrophy	XX/XX (XX.X%)	[XX% - XX%]
If yes: Valvular heart disease	XX/XX (XX.X%)	[XX% - XX%]
Cerebrovascular disease	XX/XX (XX.X%)	[XX% - XX%]
If yes: CVA/Stroke	XX/XX (XX.X%)	[XX% - XX%]
If yes: TIA	XX/XX (XX.X%)	[XX% - XX%]
Cardiac surgery	XX/XX (XX.X%)	[XX% - XX%]
If yes: CABG	XX/XX (XX.X%)	[XX% - XX%]
If yes: Valve	XX/XX (XX.X%)	[XX% - XX%]
Diabetes	XX/XX (XX.X%)	[XX% - XX%]

CONFIDENTIEL / CONFIDENTIAL

Toute reproduction ou distribution, totale ou partielle, de ce document, sans autorisation préalable de ICON PLC est interdite.
Reproduction and distribution of this document, in whole or in part, is strictly forbidden without prior authorization from ICON PLC.

STATISTICAL ANALYSIS PLAN

FARAPULSE PersAFOne SAP V1.0

PERSAFONE

Page 35 /49

Hypertension	XX/XX (XX.X%)	[XX% - XX%]
Hyperthyroidism	XX/XX (XX.X%)	[XX% - XX%]
Hypothyroidism	XX/XX (XX.X%)	[XX% - XX%]

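### The secondary stroke/TIA endpoint is read from a single event name on the adverse event form, against the SAP's own rule that committee-reviewed data take precedence

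*SAP*

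**What the plan says.** The endpoint is item 3 of Protocol 6.2, "The proportion of subjects with stroke or TIA", repeated in SAP 2.4.8.2. Its wording sets no relatedness condition and no 30-day limit.

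SAP 2.5, under the secondary safety heading, derives it in four pieces. The stroke rule opens "IF Event name='STROKE' in" and the TIA rule "IF Event name=' Transient Ischemic Attack' in"; both continue with the Adverse event form. Each requires a start date on or after the index procedure, with 'No' otherwise. The pair is then repeated with the remap date in place of the index date. Both stroke rules assign the name STROKE, and both TIA rules assign the name TIA.

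For data collected by investigators and reviewed by the committee, SAP 2.1.2 states: "The data reviewed by the CEC will prevail and will be analysed with no replacement of missing data from the CEC". Stroke and TIA fall within that rule, because Protocol 9.10 says "The CEDMC will convene during the study to screen, classify and adjudicate all adverse events reported in the subject investigation". (The SAP writes CEC and the protocol CEDMC; I take them to be the same body.)

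Elsewhere in the same block of SAP 2.5, device-related and procedure-related SAEs are built from the CEC's seriousness and relationship fields. The primary safety components come by default from the separate adjudication form (CE), where the stroke category is 'CVA'. SAP Table 12 has one standalone row for stroke and one for TIA, besides the stroke and TIA rows inside the 7-day composite.

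**The concern.** The SAP sets a precedence rule and then does not apply it to a named safety endpoint. As written, the committee can decide that an event was or was not a stroke or TIA, and the reported proportion will not move. Whether an event is a stroke, a TIA or neither is a matter of judgement, so this is where adjudication has work to do. In a descriptive study of at most 40 subjects, meant to inform later trials, the difference between no strokes and one stroke is among the first things a reader will look for.

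A second, conditional weakness is the test itself: one literal string per event, no synonyms, no coded term, and everything else set to 'No'.

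**Working it through.** The plan states no figure on this point, so there is nothing to reproduce. The check compares the rules and then sizes one error.

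**1. Which source governs.** Protocol 9.10 sends all adverse events to the committee; SAP 2.1.2 says the committee's data prevail; the stroke/TIA rules in SAP 2.5 use a form that the SAP names separately from the adjudication form, with no CEC condition. That the investigator completes the adverse event form is an inference from this separate naming and from Protocol 7.8. SAP 2.1.2 contains no exception that would cover these variables.

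**2. What the two rules give for one event.**

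| Adverse event form | CEC classification | SAP 2.5 counts | SAP 2.1.2 implies | Effect on 'stroke or TIA' |
|---|---|---|---|---|
| 'STROKE' | stroke | stroke | stroke | none |
| 'STROKE' | neither | stroke | neither | one too many |
| another term | stroke or TIA | neither | stroke or TIA | one too few |
| 'Transient Ischemic Attack' | stroke | TIA | stroke | none combined; both separate rows wrong |

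The last case is realistic: Protocol Table 4 makes an episode with symptoms under 24 hours a stroke if imaging shows infarction.

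**3. The literal match.** Of 'STROKE', 'Stroke', 'CVA', 'CVA/Stroke', 'Ischemic stroke' and 'Cerebrovascular accident', only the first satisfies an exact, case-sensitive comparison. 'TIA' fails the TIA test. The leading blank printed in the TIA literal may be only typographic. All this matters only if the field accepts such wordings.

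**4. Names and the combined endpoint.** Every after-remap event also meets the after-index condition, so the second flag is a subset of the first. Because both write to the same name, running them in the printed order would reset an event between index and remap to 'No'. Table 12 does not say which derivation feeds its row. No subject-level 'stroke or TIA' variable is derived, although that is the endpoint.

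**5. Size of one event.** With N = 40 (Protocol 3.7, the maximum), one event is 1/40 = 2.5 percentage points. With the N = 25 printed in the shells of SAP Tables 5 and 19 it is 1/25 = 4.0 points. For the intervals I follow SAP 2.1.4, assuming that the conditions for the asymptotic interval fail at 0 or 1 event.

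- 0/40, Agresti-Coull: n' = 40 + 1.96² = 43.84; p' = (0 + 1.92)/43.84 = 0.0438; half-width = 1.96 × √(0.0438 × 0.9562/43.84) = 0.0606. The interval is 0 (truncated from −1.7%) to 10.4%.
- 1/40, exact: lower limit 1 − 0.975^(1/40) = 0.06%; upper limit, the 97.5% point of Beta(2, 39), 13.2%.

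The chance of at least one true event among 40 is 1 − (1 − p)^40: 18%, 33%, 55% and 87% for assumed rates p of 0.5%, 1%, 2% and 5%.

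**The case against.** Four stronger readings are tempting, and the documents support none of them.

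- **Adjudicated strokes labelled 'CVA' will be missed.** 'CVA' is a value of a different field on a different form, so one event may be 'STROKE' on the adverse event form and 'CVA' on the adjudication form and be counted correctly in both places. The row "If yes: CVA/Stroke" in SAP Table 3 is a baseline history label, not an adverse event value. Whether the event name is free text or a pick-list is not stated. The SAP's habits hint at a list: for the posterior wall it enumerates several spellings, and for COVID deviations it searches within the text.
- **The error silently favours the device.** Investigator strokes that the committee rejects would still be counted, so the net direction is unknown. Nor need a miss stay hidden: Tables 14 and 15 report events by MedDRA term, and Listings 16 and 17 show them according to CEC review.
- **Any disagreement with the composite's stroke row is an error.** Its early-onset part, which includes stroke and TIA, covers only related SAEs within 30 days of a procedure. The secondary endpoint is wider, so some difference is expected.
- **The overlapping flags double-count.** They are nested subject-level indicators, and the after-index flag is a natural source for an overall row. The fault is the shared name and the unstated source.

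One might also argue that naming the adverse event form is a permitted exception, since the default to the adjudication form applies unless another source is indicated. That default, however, stands under the primary safety heading and does not qualify SAP 2.1.2.

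These objections remove the claims of certain under-counting and of one-way bias. They leave the contradiction over the source untouched.

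**Conclusion.** The SAP contradicts itself on the source for this endpoint, and as written a CEC reclassification to or from stroke or TIA is ignored. The proportion can be too high or too low. A further loss through unmatched wording arises only if the event name is free text. Each misclassified subject is worth 2.5 percentage points at 40 subjects, enough to turn 1/40 into 0/40 or the reverse. That size is illustrative: the documents give no stroke rate, and no hypothesis test depends on it. The conclusion assumes that the CEC and CEDMC are one body and that the adverse event form carries the investigator's entry. It warrants correction before analysis, but is not a fault in the study design.

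**What to change.** In SAP 2.5, derive stroke, TIA and one combined subject-level 'stroke or TIA' variable from the CEC-reviewed classification of all adverse events, from the index procedure through 12 months, with no relatedness or 30-day condition.

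Do not rely only on the primary-safety-endpoint criteria field. It is the only place on the adjudication form where the SAP shows a CVA or TIA category, and it may be blank for unrelated or late events. Where the form has no such category for an event, identify it by the MedDRA preferred terms for stroke/CVA and TIA, and state how this sits with the no-replacement rule in SAP 2.1.2.

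Give the after-index and after-remap flags different names, state that the after-index flag feeds the standalone rows of Table 12, and list every event on which the investigator and the CEC disagree.

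The cost is SAP wording and programming. Because the preferred terms are already planned for the adverse event tables, no new data collection is needed.
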